The Impact of Training with Whole Body EMS

NCT04288154

4/20/2022

The Impact of Training with Whole Body-EMS

Version6 : April 20, 2022

Aims and Objectives

This study will be undertaken in healthy adults who are employees at Mayo Clinic, Rochester MN

Primary Aim:

To assess the impact of training with whole body-EMS for a 16-week period of time, involving 1.0 x 20 minute training sessions per week, on peripheral endothelial function as measured using EndoPAT.

Secondary Aims:

To assess the impact of training with whole body-EMS for a 16-week period of time, involving 1.0 x 20 minute training sessions per week, on:

- i) Body mass index, waist circumference, percentage body fat and distribution, and blood pressure
- ii) Serum lipid profile, blood glucose and HbA1c, blood inflammatory markers including high sensitivity-CRP and uric acid, and novel cardiovascular markers in the blood such as fibrinogen, homocysteine and lipoprotein
- iii) VO₂ maximum (Cardiopulmonary exercise testing parameters)
- iv) Maximum strength and maximum power in chest press and leg press

- v) Symptoms of angina as measured by the Rose Questionnaire
- vi) Quality of life as measured by the LASA Questionnaire, symptoms of depression as measured by the PHQ-9 Questionnaire, and symptoms of stress as measured on the Perceived Stress Scale
- vii) Temporal changes in blood levels of creatinine kinase

Sensorimotor characteristics (visual-motor reaction time, peak knee muscular force, muscular force steadiness, and balance/posture)

Hypotheses

We hypothesize that healthy adults who are employees at Mayo Clinic, Rochester MN who undergo whole body-EMS training for a 16-week period of time, involving 1.0 x 20 minute training sessions per week, will experience:

- i) A significant improvement in peripheral endothelial function measured using EndoPAT
- ii) A significant improvement in body mass index, waist circumference, percentage body fat and distribution, and blood pressure
- iii) A significant improvement in lipid profile, blood glucose and HbA1c, blood inflammatory markers including high sensitivity-CRP and uric acid, and novel cardiovascular markers in the blood such as fibrinogen, homocysteine and lipoprotein
- iv) A significant improvement in VO₂ maximum and cardiopulmonary exercise testing parameters

- v) A significant improvement in maximum strength and maximum power in chest press and leg press

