- vi) A significant improvement in symptoms of angina as measured by the Rose Questionnaire
- vii) A significant improvement in quality of life as measured by the LASA Questionnaire, symptoms of depression as measured by the PHQ-9 Questionnaire, and symptoms of stress as measured on the Perceived Stress Scale
- viii) No significant difference in blood levels of creatinine kinase across time
- viii) A significant improvement in sensorimotor characteristics (visual-motor reaction time, peak knee muscular force, muscular force steadiness, standing balance, and overhead squatting posture)
- ix)

Methods

Trial Design

This study will consist of a **blinded randomized controlled prospective study design**, and will include 80 healthy individuals who are employees at Mayo Clinic, Rochester MN.

Excluded subjects will consist of:

- Subjects under the age of 18
- Pregnancy/or suspected pregnancy
- Subjects with a history of liver or kidney disease, acute illness, taking medications (such as glucocorticoids)
- Subjects who have conditions (such as chronic inflammatory muscular diseases or Cushing's syndrome) that affect muscle mass

- Individuals with pacemakers and implantable cardiac defibrillators
- Individuals who conduct any other type of resistance training (> 45 minutes/week)
- Individuals who have regular “high” alcohol consumption (> 80g/day on 5 days a week), or are under acute influence of alcohol, drugs narcotics, and/or painkillers
- Subjects unable to consent to or participate in the 16-week EMS intervention or be available for follow up (1).
- Subjects who report recent surgeries
- Cardiac arrhythmias
- Active medical implants
- Epilepsy
- Seizures
- Severe circulatory disorders
- Arterial circulatory disorders
- Strong bleeding tendencies (hemophilia)
- Bleeding
- Abdominal wall hernia
- Inguinal hernia
- Tuberculosis
- Tumor diseases
- Arteriosclerosis in advanced stage
- Severe neurological disorders
- Diabetes mellitus
- Febrile diseases
- Acute bacterial or viral infections
- Liver diseases
- Kidney diseases
- Cardiovascular diseases
- Coronary heart diseases
- Infected or wounded areas of the skin
- Skin cancer
- Rhabdomyolysis

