Previous studies have demonstrated dependence of the RH-PAT score on nitric oxide, confirming that reported RH-PAT scores indeed reflect changes in nitric oxide– dependent endothelial function, rather than neurohormonal activation (15). The reactive hyperemia protocol will consist of a 16-minute reactive hyperemia test, in the following sequence. A five-minute baseline measurement, after which a blood pressure cuff on the test arm will be inflated to 60 mmHg above baseline systolic blood pressure, or at least 200 mmHg for five minutes (occlusion of pulsatile arterial flow will be confirmed by the reduction of the PAT tracing to zero) after which, the cuff will be deflated, and the post-deflation PAT tracing will be recorded for an additional six minutes. The ratio of the PAT signal after cuff release compared to baseline will be calculated through a computer algorithm automatically normalizing for baseline signal, and indexed to the contralateral arm. The calculated ratio reflects the RH-PAT score (scores below 1.7 will be considered consistent with abnormal peripheral endothelial function).

Although RH-PAT scores may not be the gold standard for endothelial function, several studies have shown good correlation between these methods and more widely accepted methods of

endothelial function testing, such as intra-arterial acetylcholine infusion and brachial artery Doppler ultrasound following reactive hyperemia (11, 13, 14).

Laboratory Testing: Laboratory testing will be undertaken in all participants at baseline, and at 16-weeks follow-up in both the intervention and control group. Venous blood will be drawn for high-sensitivity CRP, uric acid, fasting glucose, HbA1c, lipid panel, lipoprotein A, homocysteine and fibrinogen. For patients in both groups, venous blood will also be tested for creatinine kinase levels at baseline, 8-weeks (halfway into the training programs), and 16-weeks (after completing each respective training program for both groups). A blood sample of approximately 30 mL will be drawn and all samples will be sent to the Mayo Clinic central laboratory for analysis.

Body Weight, Height, and Waist Circumference: Body height, weight and waist circumference will be measured using calibrated devices. Body mass index will be calculated as mass (kg)/height (m²).

VO2 MAX and Maximal Heart Rate: This will be tested using exercise treadmill testing in the conventional manner.

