This will be a randomized controlled trial in which there will be an interventional group and a control group into which individuals will be randomly assigned in a 1:1 ratio. We will match individuals, a priori, as best as possible on age (within 5 years) and sex. Baseline, demographic and risk factor distribution will be outlined in Table 1 of our analyses. The following parameters will be measured in all subjects at baseline, and at 16-weeks follow-up (immediately after completing training in either study protocol depending on which group the participant is in): peripheral endothelial function measured with RH-PAT using EndoPAT; body weight and body mass index; waist circumference; blood pressure; total cholesterol, low and high density

lipoprotein cholesterol and triglycerides, fasting blood glucose and HbA1c; high sensitivity-CRP, uric acid, fibrinogen, homocysteine and lipoprotein A; percentage body fat; maximum strength and maximum power in leg press; VO₂ maximum, maximal heart rate, and scores measured on the Rose questionnaire, LASA questionnaire, PHQ-9 questionnaire and Perceived Stress Scale. In addition, serum creatinine kinase will be measured at baseline, 8 weeks and 16 weeks.

We will compare values of each parameter between groups at baseline and after 16-weeks using unmatched analyses (using Student's t-test when comparing the aforementioned measures as continuous variable and using Chi-squared test when characterizing variables in categories of normal vs. abnormal). We will also assess for differences in the value of each parameter within groups between baseline and 16-weeks follow-up using matched analyses (using Student's paired t-test when comparing the aforementioned measures as continuous variable and McNemar's test when characterizing variables in categories of normal vs. abnormal). Lastly, we will compare the differences between baseline and 16-weeks follow-up for each parameter between groups using unmatched analyses (using the student t-test when comparing the aforementioned measures as continuous variable and using Chi-squared test when characterizing variables in categories of normal vs. abnormal).

Clinical Significance

Cardiovascular disease (CVD) is the primary cause for morbidity, mortality, and the associated rising health care costs in the world (21). According to 2012 statistics, poor diet, smoking, and

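### CK is drawn at week 8 but no planned test uses it, and the hypothesis of no significant CK difference has no margin or confidence-interval criterion

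*Combined protocol and SAP*

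**What the plan says.** Secondary aim vii is "Temporal changes in blood levels of creatinine kinase". The matching hypothesis, stated for adults who undergo EMS training, is "No significant difference in blood levels of creatinine kinase across time".

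Laboratory Testing has both groups tested for "creatinine kinase levels at baseline, 8-weeks (halfway into the training programs), and 16-weeks", and the Schedule of events agrees. Statistical Analysis repeats that "serum creatinine kinase will be measured at baseline, 8 weeks and 16 weeks".

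Statistical Analysis then plans three sets of comparisons:

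- Between groups: "We will compare values of each parameter between groups at baseline and after 16-weeks using unmatched analyses".
- Within groups: "differences in the value of each parameter within groups between baseline and 16-weeks follow-up using matched analyses".
- Change between groups: "we will compare the differences between baseline and 16-weeks follow-up for each parameter between groups using unmatched analyses".

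Continuous values get t-tests. The categorical versions of the between-group sets are described as "using Chi-squared test when characterizing variables in categories of normal vs. abnormal", with McNemar's test within groups. No significance level, repeated-measures method, CK margin or CK cut-off is given.

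**The concern.** There are two gaps between the CK objective and the CK analysis.

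First, the aim and hypothesis concern the course over time and a mid-training sample is taken for it, but the analysis reduces to two time points. A CK change present at week 8 lies outside every planned test.

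Second, the hypothesis predicts an absence of difference, and the only stated tools are significance tests. Such a test can fail to reject because CK did not move or because the estimate is imprecise, and the plan offers no way to tell these apart. This matters because Efficacy and Safety Considerations treats CK elevation as an important issue and says EMS may raise CK more than voluntary exercise does. A reassuring statement about CK should not rest on imprecision.

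**Working it through.** **Step 1: time points collected against time points analysed.** The plan states no CK figure to reproduce, so this step compares the text.

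| Item | Baseline | Week 8 | Week 16 |
|---|---|---|---|
| CK drawn, both arms | yes | yes | yes |
| Between-group comparison | yes | no | yes |
| Within-group comparison | yes | no | yes |
| Between-group comparison of change | yes | no | yes |

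The comparisons apply to every parameter, so CK at baseline and week 16 is covered. The categorical versions use the same two times. Week 8 appears in Statistical Analysis only as a measurement.

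**Step 2: what a non-significant result would leave open.** From the documents: 80 participants at 1:1, so 40 per arm. Assumed, because the documents are silent: two-sided 0.05, analysis on the log scale, log-SD (s) 0.4-0.8, correlation between visits (r) 0.5-0.7, no loss to follow-up. An increase that just misses significance has an estimate of t × SE on the log scale, so its upper 95% limit as a ratio is exp(2 × t × SE).

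| Planned comparison | SE | t | Smallest case | Largest case |
|---|---|---|---|---|
| Between arms, week 16 | s√(2/40) | 1.991 (78 df) | s 0.4: SE 0.0894, limit 1.43 | s 0.8: SE 0.1789, limit 2.04 |
| Between arms, change | s√(2(1−r))√(2/40) | 1.991 (78 df) | s 0.4, r 0.7: SE 0.0693, limit 1.32 | s 0.8, r 0.5: SE 0.1789, limit 2.04 |
| Within arm | s√(2(1−r)/40) | 2.023 (39 df) | s 0.4, r 0.7: SE 0.0490, limit 1.22 | s 0.8, r 0.5: SE 0.1265, limit 1.67 |

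For example, exp(2 × 1.991 × 0.0894) = exp(0.356) = 1.43. With 34 per arm (an assumed 15% loss), the same formulas give 1.47-2.17, 1.35-2.17 and 1.24-1.75.

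The same point can be made without assuming an SD. With 40 per arm, a true between-arm difference of 0.4 SD has power 0.42 (non-central t, non-centrality 0.4 × √20 = 1.79), so it is missed about 58% of the time. A within-arm rise of 0.4 SD of the change has power 0.69 and is missed about 31% of the time.

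**Step 3: what week 8 would add for a sustained change.** Let r0 be the correlation of each follow-up value with baseline, and r1 the correlation between weeks 8 and 16. After baseline adjustment, the variance using the mean of both visits relative to week 16 alone is ((1 + r1)/2 − r0²)/(1 − r0²).

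- Equal correlations of 0.5: (0.75 − 0.25)/0.75 = 0.667, a 33% saving.
- Equal correlations of 0.7: (0.85 − 0.49)/0.51 = 0.706, a 29% saving.
- r0 = 0.5, r1 = 0.8: (0.90 − 0.25)/0.75 = 0.867, a 13% saving.
- r0 = 0.5, r1 = 0.9: (0.95 − 0.25)/0.75 = 0.933, a 7% saving.

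The gain is real, but its size depends on a correlation that the documents do not give.

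**The case against.** The strongest reply is that CK is one of many secondary outcomes, the week-8 samples are already scheduled, and nothing stops the investigators from summarising them. The plan states no rule that a non-significant p-value will count as support, and the wording may simply mirror the other hypotheses, which all predict a significant improvement. This limits the severity. It does not close either gap: an analysis chosen after seeing the data is weaker than one sentence written now, and the hypothesis itself is worded in terms of non-significance.

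The ratios above also rest on assumed variability and on a log scale that the plan does not specify. They are illustrations; the comparison of time points in the text needs none of them.

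A fair practical objection is that a contrast between weeks 8 and 16 may reflect when blood was drawn. Efficacy and Safety Considerations reports raised values lasting from 24 hours to 4 days. The Schedule of events allows ±7 days at both follow-up visits, and no interval from last session to draw is fixed. This stands, and the fix takes it up.

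**Conclusion.** The point holds on the text. No planned comparison uses the week-8 CK, and the hypothesis of no significant difference has no margin or confidence-interval criterion. Under the stated assumptions, a result just short of significance would remain compatible with a between-arm ratio as high as 1.32-2.04, depending on the comparison, or a within-arm rise of 22-67%. It should be fixed, but it concerns one secondary aim. The primary EndoPAT conclusion is unaffected.

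Stronger readings are not supported:

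- **A reader might infer that CK will peak at week 8 and be back down by week 16.** The documents do not predict that course. Acclimatisation in as little as 3 weeks would be under way before week 8. The guideline that the highest level comes no earlier than 8-10 weeks would, if anything, favour week 16, and it is a general consensus statement rather than this trial's stated progression.
- **A reader might infer steady escalation of intensity from week to week.** Intervention describes small increases within each session to hold or slightly raise perceived exertion, from start settings determined after 4, 8 and 12 weeks.
- **A reader might infer that a normal-versus-abnormal CK analysis is already defined.** The categorical option is generic, and no CK cut-off appears.
- **A reader might infer that the investigators will treat non-significance as proof.** The plan permits that reading but does not state it.

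**What to change.** 1. In Statistical Analysis, add a CK analysis using all three time points in both arms. One suitable choice is a repeated-measures model of log CK at weeks 8 and 16 with arm, visit, arm-by-visit and baseline log CK. Report the EMS/control ratio at each visit and the within-arm ratio to baseline at each visit, with 95% confidence intervals.
2. If the normal-versus-abnormal comparison is applied to CK, include week 8 and use the laboratory's reference limit, as stated in advance by the investigators.
3. Reword the CK hypothesis as estimation of the change over time, and state that p > 0.05 will not be taken as evidence of no change. A pre-stated margin, of the investigators' choice and judged by the upper confidence limit, is needed only if they wish to claim no important rise.
4. Record the time from the last session to each CK draw, so that the week-8 and week-16 values can be interpreted.

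The cost is one added model, a reworded hypothesis and one recorded time per draw. No new samples are needed. The downside is a little more analysis and a more modest CK conclusion.

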All subjects in both groups who enroll into this study will undergo an assessment of peripheral endothelial function with reactive hyperemia-peripheral arterial tonometry (RH-PAT) testing using EndoPAT; an assessment of vital signs including heart rate, blood pressure, weight, height and body mass index; laboratory blood work; cardiorespiratory testing using treadmill testing to determine VO₂ max and maximal tolerated heart rate; maximal strength and maximal power

testing on chest press and leg press testing; and ultrasound-based percent body fat and fat distribution testing at baseline, and at 16-weeks follow-up (immediately after completing a 16-week training program using whole body-EMS) (**Figure 1**). Baseline cardiovascular risk factors will be assessed by subject questionnaire and verified by chart review. In addition, subjects will complete an angina/chest pain symptom questionnaire (Rose Questionnaire), quality of life questionnaire (LASA Questionnaire), depression questionnaire (Patient Health Questionnaire-9) and perceived stress questionnaire (Perceived Stress Scale) to assess for psychosocial wellness at each point in the study. Women of childbearing potential will have a urine pregnancy test to rule out pregnancy prior to enrollment. Sensorimotor characteristics such as visual-motor reaction time, Other sensorimotor characteristics (standing balance and posture) will be examined using a force plate and 2D camera with a commercially available app. . . . Standing balance will be assessed by subjects standing on two legs for 30 seconds eyes-open and –closed. . Overhead squatting posture will be examined by analyzing static pictures of performing subjects with ipad-based postural assessment application (Posture Co, Inc, Trinity, FL, USA).

Intervention

Individuals who enroll in this study will be randomized to two groups, in a 1:1 ratio: intervention group and control group. In the intervention group we will apply 16-weeks of conventional whole body-EMS training 1.0 time a week for a maximum of 20 minutes per session, with no intermittent breaks. Individuals will undertake routine exercise maneuvers (including squatting, lunging, forward flexion etc.) under the guidance of certified trainers while simultaneously having percutaneous electrical stimulation applied to their bodies while exercising through the

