and guided by two certified instructor (i.e., two applicants coached by one instructor). Whole body-EMS will be conducted on approximately the same day, once a week (i.e., $1.0 \times \text{week}$) for 20 minutes. The device will apply a bipolar electric current; we will select an impulse frequency of 85 Hz, an impulse width of 350 μs , and will apply an interval approach with 4 seconds of stimulation alternating with 4 seconds of rest. Gentle slight dynamic exercises will be performed during the 4-second stimulation phase. Each session will consist of 10–14 dynamic exercises structured in one to two sets of eight repetitions performed without any additional weights in a standing position. Most exercises will be based on a low amplitude squat exercise ($< 35^\circ$ leg flexion) with full amplitude movements of the arms (such as rowing, lat pulley, or butterfly). The emphasis of the protocol however will not be the effect on muscles induced by voluntary activation but by the application of whole body-EMS with high current intensity during functional movements. During the course of the study, the instructor will progressively increase the volume of stimulation by extending the length of the session from 14 up to 20 minutes after 4 weeks of training. The intensity of the stimulation will be regulated using a rate of perceived exertion (RPE) scale to generate a sufficient, but tolerable, intensity of EMS application to all stimulated areas. For each of the muscle groups stimulated, participants will be encouraged to exercise at a RPE of “6–7 out of 10” (i.e., “hard+ to very hard”) on the Borg CR10 Scale (5). This specification will be achieved in close interaction between the participant and instructor. Based on initial start settings determined after 4, 8, and 12 weeks, the impulse intensity will be increased slightly every 3 minutes to maintain/slightly increase the prescribed RPE during each session (**refer to Supplemental Video**).

Schedule of events

| | Baseline Day 0 | Weeks 1-7 | Week 8 follow-up (+/- 7 days) | Weeks 9-15 | Week 16 follow-up (+/-7 days) |
|---|----------------|-----------|-------------------------------|------------|-------------------------------|
| Informed Consent | X | | | | |
| Brief review of medical history | X | | | | |
| Exercise with EMS device | X | X | X | X | X |
| Blood draw and laboratory testing** | X | | | | X |
| Creatinine Kinase | X | | X | | X |
| Physical Assessment* | X | | | | X |

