Thus, EMS has to be applied intelligently and carefully, especially in untrained subjects who have to be trained with caution because of their lower resistance to intensive loads. Overloading the subjects' muscular system by for example applying EMS with high stimulation intensity in combination with not enough regeneration time between sessions could inhibit or delay strength adaptations. This must be balanced against the fact that employing a load that is too low can result in a rapid decrease (within 2–4 weeks) in achieved strength gains, or to a lack of any significant enhancements in post-testing (88). Nevertheless, significant strength gains have been demonstrated in individuals training appropriately with EMS after a period of only 2–6 weeks (88). Several trials have also shown that when EMS is applied with optimal loads, the achieved strength gains can be kept at a constant level, amongst untrained and trained subjects, for up to 4 weeks after post-testing without doing any exercise (88).

Guidelines for safe and effective WB-EMS

In general:

1. Safe and effective Whole-Body-EMS Training must always be accompanied by a trained and licensed WB-EMS trainer or scientifically trained personnel familiar with this field of application.
2. Before the first training session of every beginner, an anamnesis of possible contraindications based on a list of questions must be taken and then documented in

writing, confirmed by the client's signature and archived. Where relevant anomalies are found, a doctor is to be consulted and training only be commenced if clearance has been given.

Preparing for training:

1. As with any kind of intensive training, Whole-Body EMS training must only be carried out in a good physical condition and free of pain. This includes abstaining from alcohol, drugs, stimulants/muscle relaxants or stress ahead of the training session. Training must never be carried out by anybody suffering from an illness with fever.
2. Whole-Body EMS training leads to very high metabolic stress of the organism because of very high volume of muscle mass addressed. This factor has to be taken into account through sufficient food intake that is as high in carbohydrates as possible. If this is not possible, then at least a high carbohydrate, but light snack (≈ 250 kcal) should be eaten, ideally about 2 hours before training.

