3. So as to avoid possible renal stress (especially with undiagnosed problems) through intensive WB-EMS, additional fluids should be consumed before/during and after training (500 ml each).
4. Generally, medical – ideally sport-medicinal – consultation and clarification is advisable in the case of any discomfort, physical restrictions, infections or other internal, cardiological or orthopedic illnesses.

Training:

1. Regardless of physical status, sport experience and the user's wishes to that effect, under no circumstances may WB-EMS training to exhaustion take place during the first training session or trial training. This has led in the past to undesired side effects and negative health consequences and so must be avoided at all costs.
2. After moderate initial WB-EMS, the stimulation level or current must be successively increased and adapted to the individual goals. The highest level is to be reached only after 8-10 weeks of systematic training at the earliest (user's subjective effort impression: hard-hard+). Training to complete exhaustion, especially in the sense of painful, continuous tetanus during the current phase, must generally be avoided.
3. In addition, the initial training should be conducted with a reduced effective training period. Advisable is 5 min impulse familiarization and a curtailed training session with moderate stimulus intensity (user's subjective effort impression: a bit hard) and 12 min intermittent load with short impulse phase (\square). Only then should the training duration be cautiously increased and never exceed 20 minutes.

4. To ensure sufficient conditioning and to minimize or rule out possible health impairments, training frequency may not exceed one training unit per week during the first 8-10 weeks.
5. Even after this conditioning phase, an interval of ≥ 4 days must be maintained between training units in order to avoid accumulation of muscle breakdown products, permit regeneration and adaptation and thus ensure a successful training outcome.

Safety aspects during and after training

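### Acute illness is screened at entry but not at the week-16 tests, which shifts the paired hs-CRP change upward and adds noise to the between-group comparison (minor)

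*Combined protocol and SAP*

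**What the plan says.** **Entry.** Methods, Trial Design lists "Acute bacterial or viral infections" among the exclusions, together with febrile diseases and acute illness. Baseline values therefore come from people selected to be free of acute illness.

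**Week 16.** The schedule of events has the row "Brief review of medical history | X", marked in the Day 0 column only. Outcomes and Measurements schedules follow-up tests around when subjects and equipment are free, and does not mention health status. The EndoPAT section controls fasting, coffee, tobacco and vasoactive drugs on the test day, but not illness. Laboratory Testing draws hs-CRP and fibrinogen at both time points with no illness condition.

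**Rules that continue after baseline.** Guidelines for safe and effective WB-EMS, largely repeated in Figure 4, says "Training must never be carried out by anybody suffering from an illness with fever". It also requires good physical condition for training, says that medical "clarification is advisable in the case of any discomfort, physical restrictions, infections or other internal, cardiological or orthopedic illnesses", and has the trainer check each user around every session. All of this concerns training.

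**Analysis.** Statistical Analysis states: "We will also assess for differences in the value of each parameter within groups between baseline and 16-weeks follow-up using matched analyses". It also plans t-tests between groups at each time point and on the change. It names no main analysis and no transformation for hs-CRP.

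**The concern.** The two ends of each paired comparison are taken under different selection rules: illness is filtered out at baseline and not at week 16. Hs-CRP is an inflammatory marker, so a participant bled during or just after an infection may give a very high value. Hypothesis iii expects inflammatory markers to improve in people who train with EMS, which is worded as a within-group change, and the plan tests such changes with a paired t-test. Illness at week 16 only would push that change upward in both arms. An untransformed t-test is also sensitive to a few extreme values, so the between-group test could lose power.

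**Working it through.** **Inputs from the documents.** The trial "will include 80 healthy individuals who are employees at Mayo Clinic, Rochester MN", and "Individuals who enroll in this study will be randomized to two groups, in a 1:1 ratio", so there are 80/2 = 40 per arm. The plan gives no power calculation, SD, hs-CRP distribution or illness rate, so it has no figure of its own to reproduce.

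**Assumptions.** Two-sided alpha is 0.05. Hs-CRP is log-normal with median 1 mg/L, log-SD 0.9 and within-person correlation 0.7 on the log scale. A share p = 2-10% of each arm is ill at week 16, and illness multiplies hs-CRP by k = 2 to 10. The true EMS effect is a 30% reduction.

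**1. Will anyone be ill?** The chance of at least one ill participant among 80 is 1 - (1 - p)^80. That is 80% at p = 2%, 98% at 5% and over 99.9% at 10%. The expected number per arm is 40p = 0.8, 2 or 4.

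**2. Within-group shift.** The illness-free mean is exp(0.9²/2) = exp(0.405) = 1.50 mg/L. With no treatment effect, the mean change moves by p × (k - 1) × 1.50:
- k = 2: 0.03 mg/L (p = 2%) to 0.15 (p = 10%)
- k = 10: 0.27 mg/L (p = 2%) to 1.35 (p = 10%)

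The shift is upward in both arms, against hypothesis iii. In a second model, illness adds an exponentially distributed amount with mean 10 or 30 mg/L. There the paired test declared a false worsening in about 2-18% of runs, against 2% without illness.

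**3. Between-group power, log scale.** The variance of the log change is 2 × 0.81 × (1 - 0.7) = 0.486, so the SD is 0.70. The effect is |ln 0.7| = 0.357, giving d = 0.357/0.697 = 0.51. Illness adds p(1 - p)(ln k)² to the variance:
- p = 2%, k = 2: adds 0.0196 × 0.480 = 0.009, which is almost nothing.
- p = 10%, k = 10: adds 0.09 × 5.30 = 0.477, so the SD is √0.963 = 0.98 and d = 0.36.

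By simulation, power goes from about 0.61 without illness to 0.37-0.60.

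**4. Between-group power, raw scale.** Simulated, with p = 2-10%:

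| Illness rise | Power (about 0.33 without illness) |
|---|---|
| 2-fold | 0.33 |
| 3-fold | 0.28-0.31 |
| 5-fold | 0.19-0.29 |
| 10-fold | 0.11-0.21 |

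**5. False positives.** With equal illness in both arms and no treatment effect, the between-group type I error was 0.03-0.05. In the second model it was 0.017-0.036 on the raw scale, against 0.044 without illness. Illness makes the raw test conservative.

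**6. EndoPAT and VO2 max.** With 40 per arm, 80% power corresponds to d = (1.96 + 0.84) × √(2/40) = 0.63. Assume illness moves the result by 0.5-1 SD in 2-10% of participants. The within-arm shift is then 0.02 × 0.5 = 0.01 SD to 0.10 × 1 = 0.10 SD. The SD grows by at most √(1 + 0.09) = 1.044, and power falls from 0.80 to 0.77-0.80.

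**The case against.** **Illness is not ignored after baseline.** The training guidelines apply at every session, and the schedule puts an EMS session in the same week-16 column as the blood draw and EndoPAT. A visibly ill participant would often be noticed. This stands as partial cover, so it would be wrong to infer that nothing applies after Day 0. But the absolute bar covers only illness with fever, consultation for infections is only advised, and nothing tells staff to defer or flag a test. The visit window is ±7 days and EndoPAT may follow up to two weeks after training ends, when no trainer is checking.

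**Randomisation protects the treatment contrast.** This stands. Participants and investigators are blinded, and the sham arm does a similar exercise programme, so illness is expected equally in both arms. A reader might infer that a few infections could bias the EMS effect or create a spurious one. The documents do not support that: illness that does not depend on arm adds noise, and the type I error does not rise.

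**The loss may be small, and part of it is a scaling problem.** This also stands. A 2-fold rise costs almost nothing, and the large losses need rises near 10-fold. In this model, moving hs-CRP to the log scale takes power from about 0.33 to 0.61 with no illness at all, more than an illness check could recover. The log scale does not remove the loss, however: log-scale power still falls to 0.37 at the worst corner.

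**Conclusion.** The gap is real and minor. Entry screening for acute illness has no counterpart at the week-16 tests. For hs-CRP this shifts the paired change upward, by 0.03 to 1.35 mg/L under the stated assumptions, and costs the between-group comparison anything from nothing to about two thirds of its raw-scale power (0.33 to 0.11). Fibrinogen may behave similarly but was not quantified. The range is wide because illness rate, illness effect and hs-CRP spread are all assumed.

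Two stronger readings should be resisted. One is that illness will swamp the hs-CRP comparison; that holds only near the 10-fold assumption, which the documents do not supply. The other is that the primary endpoint is compromised; with illness effects of 0.5-1 SD, the effect on EndoPAT and VO2 max is negligible. For hs-CRP, the within-group shift runs against the hypothesis, so it cannot manufacture an apparent benefit.

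**What to change.** - At the week-16 visit, with staff blind to arm, repeat the entry question on acute illness, fever and infection before testing, and record the answer.
- If the answer is positive, defer the blood draw, and for consistency the other tests, within the windows already allowed: ±7 days for the visit, and two weeks after the end of training for EndoPAT.
- If recovery falls outside the window, test where the protocol otherwise permits and flag the value, so that data are not lost.
- Prespecify a between-group sensitivity analysis of hs-CRP without flagged values. It should stay a sensitivity analysis, because the flag arises after randomisation.
- Prespecify the log scale for hs-CRP.

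The cost is one question per participant, a sentence or two in Statistical Analysis, and a few tests moved by some days. Illness status that is not recorded at the visit is hard to recover later, so the question should be in place before week-16 testing.
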